Appendix 3 – PROTOCOL SIGNATURE PAGE, ADVANCE Registry.....	19

I. BACKGROUND AND RATIONALE

II. FFR_{CT}

III. REGISTRY OBJECTIVE

The objective of the HeartFlow ADVANCE Registry is to evaluate utility, clinical outcomes, and resource utilization of FFR_{CT}-guided evaluation in clinically stable, symptomatic patients with CAD in order to further inform patients, health care providers, and other stakeholders about which technologies are most effective and efficient in the diagnosis and management of CAD.

SPECIFIC OBJECTIVES:

1. To determine if the availability of FFR_{CT}, in addition to coronary anatomy from the cCTA, will lead to a significant change in the coronary management plan.
2. To assess the real world outcomes of utilizing FFR_{CT} to guide invasive management and/or medical treatment.
3. To assess resource utilization, following standard practice for diagnostic and treatment pathways incorporating FFR_{CT} as the preferred CAD diagnostic test.
4. To provide society including patients, health care providers, and other stakeholders with information about which diagnostic technologies are most effective and efficient in managing patients with CAD.

IV. REGISTRY ENDPOINTS

IV. A. Primary Endpoints

The primary endpoint of the ADVANCE Registry is the reclassification rate between the coronary management plan based on the review of the cCTA compared to the management plan based on FFR_{CT} when obtained, as assessed by an independent review committee.

IV. B. Secondary Endpoints

The secondary endpoints of the ADVANCE Registry include the following:

- a. Rate of reclassification between Investigator management plan based on cCTA alone compared to actual clinical management within 90 days.
- b. Rate of invasive catheterization without obstructive disease at 90 days.
- c. Percent of patients undergoing revascularization within 90 days for whom functional data are available prior to revascularization.
- d. Major Adverse Coronary Event (MACE) rates at 90 days, 180 days, 1 year, and 3 years. MACE is defined as the composite rate of all cause death, non-fatal myocardial infarction (MI) and unplanned hospitalization for acute coronary syndrome (ACS) leading to urgent revascularization.

- e. Individual components of MACE (all cause death, non-fatal MI, unplanned hospitalization for ACS leading to urgent revascularization) at 90 days, 180 days, 1 year, and 3 years.
- f. Estimated cumulative medical radiation exposure at 1 year.

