FFR_{CT} utilizing cCTA data, is a commercially available technology in the locations where the registry will be conducted, and will be used in the manner in which the product has been authorized for marketing and within the authorized intended use and subject population. FFR_{CT} analysis will be performed using the required cCTA data-set for these subjects. The FFR_{CT} analysis does not require additional imaging or image acquisition protocols, therefore is not expected to present any additional clinical risks to subjects.

X. STATISTICAL CONSIDERATIONS

X. A. General Considerations

Tabulations of summary statistics, graphical presentations, and statistical analyses will be performed using SAS[®] software or an equivalent. Data obtained from clinical records and entered into the eCRF database will be provided in separate data listings showing individual subject values. The Steering Committee will work on the planning and reporting of statistical analyses by preparing a fully defined statistical analysis plan.

X. B. Subject Characteristics

Subject accountability will be described, including number of subjects enrolled, the number included in the analysis, and reasons for any subjects discontinued from the study or not included in the analysis. Demographic information will be summarized using descriptive statistics. Gender will be summarized by counts and percentages. Medical histories will be summarized by counts and percentages.

X. C. Endpoint Analysis

X. C. 1. Analysis of Primary Endpoint

The primary endpoint is the reclassification rate between the coronary management plan based on the review of the cCTA alone compared to the management based on FFR_{CT} when obtained, as assessed by an independent review committee.

X. C. 2. Analysis of Secondary Endpoints

Descriptive statistics for the secondary endpoints will be provided. Rates of MACE and each component of MACE, at each follow-up (90 days, 180 days, 1 year, and 3 years) post-procedure and annually thereafter) will be estimated.

X. D. Analysis Populations

Intent-to-Diagnosis (ITD): All patients who meet the registry criteria, sign the written informed consent, and are enrolled in the registry, will be counted in the ITD set, which will be the primary analysis set.

Per-Protocol (PP): The ITD sample excluding patients who are “deregistered” or do not meet certain key entry criteria.

X. E. Procedures for Reporting Deviations from Original Statistical Plan

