The eCRF captures some of the data critical to the event adjudication. However, there will still be a need for supporting documentation from the sites in order to render an adjudicated result. The eCRF data and supporting documentation are completely anonymized by each site and identified only with the subject ID.

Events will be adjudicated by the CEC according to pre-specified criteria. The CEC adjudicated data will be used in the analyses unless otherwise stated.

XIII. H. Endpoint Review Committee

An Endpoint Review Committee, consisting of independent physicians not participating in the diagnosing, planning, or treatment of subjects in the registry will be used to adjudicate the primary endpoint. The Committee will document the treatment management plan following review of the cCTA and again, following review of the enrolling FFR_{CT} for all patients in whom cCTAs and FFR_{CTs} are available.

XIV. FINAL REPORT

Following conclusion of the registry, a final report shall be written by HeartFlow or its designee and distributed to all investigators. This final report shall account for all enrolled subjects.

Appendix 1 - REGISTRY DEFINITIONS**Appendix 2 – REFERENCES****Appendix 3 – PROTOCOL SIGNATURE PAGE, ADVANCE Registry****SPONSOR APPROVAL**

This protocol has been reviewed and is approved by HeartFlow.

Date

HeartFlow, Inc.

SITE APPROVAL

Site Number: _____ Site Name: _____

I have read and understood the HeartFlow Registry Protocol titled “The HeartFlow ADVANCE Registry: Assessing Diagnostic Value of Non-invasive FFR_{CT} in Coronary Care” and agree to follow the procedures and requirements.

Print Name

Signature

Date

Statistical Analysis Plan for Heartflow ADVANCE Registry

By signing this document, I am confirming that I have reviewed and approve the analysis plan referenced above.

Principal Investigator

Signature

Date (mm/dd/yyyy)

Principal Investigator

Signature

Date (mm/dd/yyyy)

Heartflow

Signature

Date (mm/dd/yyyy)

Statistical Analysis Plan: Heartflow ADVANCE Registry

I. Study Overview

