cCTA is a non-invasive test used to diagnose the severity of coronary artery disease. FFR_{CT} is a non-invasive test that can be added to cCTA. This study seeks to describe the findings of each test and describe how adding FFR_{CT} would change the management plan indicated by cCTA. The study also seeks to describe subject outcomes, radiation exposure, and additional cardiac testing needs for subjects by whether they were planned for medication only, PCI, or CABG.

II. Study Objectives

- A. Summarize baseline demographics and subject characteristics overall and by whether FFR_{CT} results were available
- B. Summarize the extent of disease in each vessel measured by cCTA and FFR_{CT}
- C. Summarize the changes in coronary therapeutic management strategy before and after considering both cCTA and FFR_{CT} and report the proportion of intended strategies that were changed.
- D. Compare invasive catheterization (ICA) and revascularization rates between enrollment and the 90 day assessment based on the findings from cCTA and FFR_{CT}
- E. Determine whether major adverse coronary event rates during follow-up differ according to treatment plan and testing findings
- F. Summarize the estimated cumulative radiation exposure
- G. Determine whether the time to first cardiovascular test during follow-up differs according to management strategy

IV. General Methodology

Most of the analyses will be descriptive. Unless noted otherwise, categorical variables will be presented as number and percentage and continuous variables will be presented as median (25th, 75th percentile). Kaplan-Meier methods will be used to report event rates that occur during follow-up. The key objectives that will involve statistical testing are the relationships between having an invasive procedure or revascularization and the findings from cCTA and FFR_{CT}.

V. Subject Accountability and Characteristics

VI. Sample Size Determination

VII. Definitions

VIII. Endpoint Analyses

A. Primary Endpoint: The proportion of coronary management plans that were changed when core lab FFR_{CT} coronary anatomy findings were added to the core lab cCTA findings

B. Secondary Endpoints

- i. Secondary Endpoint 1: The proportion of coronary management plans that were changed when site reported lab FFR_{CT} coronary anatomy findings were added to the site reported lab cCTA findings
- ii. Secondary Endpoint 2: Vessel level findings from cCTA and FFR_{CT}

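### Does naming all enrolled patients as the primary analysis set dilute the primary reclassification rate?

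*Combined protocol and SAP*

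**What the plan says.** Protocol X.D defines the Intent-to-Diagnosis (ITD) set as patients who meet the criteria, consent and are "enrolled in the registry, will be counted in the ITD set, which will be the primary analysis set". It does not require an FFRCT result. The inclusion criteria in V.D ask for eligibility for FFRCT, not for a completed analysis.

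The primary endpoint in IV.A is the rate of reclassification of the cCTA-based plan "compared to the management plan based on FFR_{CT} when obtained". Section X.C.1 repeats the condition: "the management based on FFR_{CT} when obtained, as assessed by an independent review committee". Section XIII.H sets the committee's task: it records a plan after the cCTA and again "following review of the enrolling FFR_{CT} for all patients in whom cCTAs and FFR_{CTs} are available".

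The SAP expects some patients to lack FFRCT. Objective A summarises baseline characteristics "overall and by whether FFR_{CT} results were available". SAP VIII.A states the primary endpoint as the proportion of plans that changed once core lab FFRCT findings were added to core lab cCTA findings. It names no analysis set in the visible text.

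The Per-Protocol (PP) set in X.D removes deregistered patients and those who "do not meet certain key entry criteria". It is not worded in terms of FFRCT availability.

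**The concern.** Read alone, X.D puts every enrolled patient into the primary analysis, including those for whom the committee never wrote a second plan. An analyst who applied it literally might keep those patients in the denominator and, with no recorded change, count them as unchanged. The headline rate would then fall in proportion to the share without FFRCT. An analyst who left them out would be using a smaller set than the one X.D calls primary.

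The two denominators answer different questions. One is how often FFRCT changes the plan when there is a result. The other is how often a strategy of ordering FFRCT changes the plan, with missing results included. If the text left the choice open, it could be made after both figures were known. The PP set offers no obvious way out, because it does not select patients with FFRCT and its entry-criteria exclusion overlaps with a condition already built into ITD.

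**Working it through.** The documents give no reclassification rate, no expected FFRCT availability and no visible sample size, so there is no planned figure to reproduce. The size of the effect can be shown only on assumed inputs.

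**Inputs (both assumed)**
- r: reclassification rate among patients with both committee plans.
- a: share of ITD patients with an FFRCT result.

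**Three ways to treat ITD patients without FFRCT**
1. Left out of the denominator: rate = r.
2. Kept and counted as unchanged: rate = r × a, a shortfall of r × (1 − a).
3. Kept and counted as changed: rate = r × a + (1 − a).

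**Results for r = 0.60**

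| a | Left out | Counted as unchanged | Counted as changed |
|---|---|---|---|
| 0.80 | 60% | 0.60 × 0.80 = 48% | 48% + 20% = 68% |
| 0.90 | 60% | 0.60 × 0.90 = 54% | 54% + 10% = 64% |
| 0.95 | 60% | 0.60 × 0.95 = 57% | 57% + 5% = 62% |
| 1.00 | 60% | 60% | 60% |

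Over wider assumed ranges, the shortfall under the second treatment runs from 0.20 × 0.05 = 1 point (r = 0.20, a = 0.95) to 0.80 × 0.30 = 24 points (r = 0.80, a = 0.70). It is zero when a = 1. It is also zero under the first treatment, whatever the value of a.

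**Which treatment the text supports**
- IV.A and X.C.1 make the comparison conditional on FFRCT having been obtained. That limits who has an endpoint value.
- XIII.H has the committee record the pair of plans only where both tests are available, so no committee-assessed change or absence of change exists for anyone else.
- SAP VIII.A speaks of plans changed when FFRCT findings were added. A plan to which none were added falls naturally outside that proportion.
- X.B reports the number enrolled separately from the number analysed, with reasons for those left out. The protocol thus foresees an analysed number below the enrolled number.
- No visible passage scores a patient without FFRCT as unchanged, or as changed.

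The passages agree on the first treatment. X.D says which patients belong to the analysis, and the endpoint definition says which of them have a value. The two can be read together without contradiction.

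**The case for a change.** The best case for a change is that this is the headline result of a registry whose sponsor, or its designee, analyses the data, and that no sentence in X.D or SAP VIII.A states the denominator. X.B is an accountability rule and does not define a denominator. X.E requires a SAP only before database lock, and asks for deviations to be reported, which is harder to apply when the planned denominator is implied. SAP XI declares no changes from the protocol, so ITD formally remains primary. An available-case rate may also be unrepresentative if FFRCT availability depends on image quality or extent of disease. One sentence would cost almost nothing.

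Part of this stands. The denominator has to be read from several places, and a single sentence would be tidier. But that sentence would say what those places already imply, so the primary result would not change. On representativeness, SAP Objective A already sets out the baseline comparison by FFRCT availability, so a reader can judge the excluded group. An all-enrolled companion rate would answer a question that neither document poses for the primary endpoint. The visible text attaches no test or threshold to the primary rate, and SAP IV describes most analyses as descriptive, so no decision depends on a few points either way.

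The PP argument is weaker. The overlap with ITD is arguable for patients failing entry criteria, but nothing in X.D removes deregistered patients from ITD, and the visible text does not define that term. Rewording PP would leave the primary rate as it is. Finally, SAP V to VII and protocol Appendix 1 can be seen only as headings. A denominator rule could sit there, and its absence from view does not show a gap in the plan.

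**Conclusion.** The mismatch in wording is real, but the feared understatement does not follow from it. Dilution needs a scoring rule that no visible passage contains. Its size (6 points at r = 0.60 and a = 0.90) rests wholly on two assumed inputs together with that rule. Read as a whole, the plan gives the rate among patients with both committee plans, with exclusions counted and explained and baseline characteristics shown by FFRCT availability. That is a sound descriptive estimate of how often FFRCT changes management when a result exists. What remains is missing detail that analysts fill sensibly from the endpoint definition and the committee's remit. No change is needed. This conclusion assumes that the text not shown contains no rule counting patients without FFRCT as unchanged.

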- g. Resource utilization composite at 90 days, 180 days, 1 year, and 3 years:
 - a) Invasive diagnostic and therapeutic coronary procedures
 - b) Treatment of MACE events
 - c) Noninvasive cardiac testing

V. C. Subject Selection

All clinically stable, symptomatic patients diagnosed with CAD by cCTA, that meet eligibility criteria, and are able and willing to participate are candidates for the ADVANCE Registry. Those patients that meet all inclusion/exclusion criteria and who sign the EC/IRB approved informed consent will be enrolled in the registry. FFR_{CT} shall be used in accordance with the current Instructions for Use document.

V. D. General Inclusion & Exclusion Criteria

Inclusion Criteria:

- 1. Provide written informed consent
- 2. Clinically stable, symptomatic patients who undergo cCTA and are diagnosed with CAD and meet eligibility criteria for FFR_{CT}.

Exclusion Criteria:

- 1. cCTA showing no CAD
- 2. Uninterpretable cCTA by site assessment, in which severe artifacts prevent angiographic evaluation
- 3. Any active, serious, life-threatening disease with a life expectancy of less than 1 year
- 4. Inability to comply with follow-up requirements

VI. H. Invasive Catheterization without Obstructive Disease

Invasive catheterization without obstructive disease will be measured by either site read coronary angiogram showing no stenosis of $\geq 50\%$ or no invasively-measured FFR ≤ 0.80 in a segment distal to a stenosis.

VII. A. Rules for Subject Withdrawal

Each subject is free to withdraw from the registry at any time. Investigator(s) also have the right to withdraw subjects from the registry in the event of illness, death or serious injury, other reasons concerning the health or wellbeing of the subject, or in the case of lack of cooperation. Should a subject decide to withdraw or should the investigator(s) decide to withdraw the subject, all efforts will be made to complete and report the observations up to the time of withdrawal as thoroughly as possible. A complete final evaluation at the time of the subject's withdrawal should be made and an explanation given as to why the subject is withdrawing or being withdrawn from the registry. All data collected up to the point of

withdrawal will remain in the study database and will be included in the analysis.

The reason for withdrawal must be noted in the eCRFs.

VII. B. Rules for terminating the registry

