- iii. Secondary Endpoint 3: Invasive catheterization and revascularization rates 90 days post enrollment
- iv. Secondary Endpoint 4: Major adverse coronary event (MACE) rates during follow-up
- v. Secondary Endpoint 5: Estimated cumulative radiation exposure
- vi. Secondary Endpoint 6: Cardiovascular testing rates during follow-up
- vii. Secondary Endpoint 7: Result from first post-baseline ICA

IX. Safety Analyses

Not applicable

XI. Changes from the Study Protocol Reflected in this Analysis Plan

None

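### Kaplan-Meier rates for the two non-fatal MACE components and for first cardiovascular test will slightly overstate the share of patients affected if deaths are censored

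*Combined protocol and SAP*

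**What the plan says.** SAP section IV (General Methodology) describes most analyses as descriptive and states: "Kaplan-Meier methods will be used to report event rates that occur during follow-up". It separates these rates from the tested questions: "The key objectives that will involve statistical testing are the relationships between having an invasive procedure or revascularization and the findings from cCTA" and FFR_CT.

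The rates that the Kaplan-Meier rule covers include:

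- **MACE and its components.** Protocol section IV.B lists the components as a secondary endpoint in their own right: "Individual components of MACE (all cause death, non-fatal MI, unplanned hospitalization for ACS leading to urgent revascularization". Protocol section X.C.2 gives the time points: "Rates of MACE and each component of MACE, at each follow-up (90 days, 180 days, 1 year, and 3 years) post-procedure".
- **Cardiovascular testing.** SAP section VIII.B, Secondary Endpoint 6, is "Cardiovascular testing rates during follow-up". SAP objective G is "Determine whether the time to first cardiovascular test during follow-up differs according to management strategy".

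SAP objective E concerns composite MACE: "Determine whether major adverse coronary event rates during follow-up differ according to treatment plan and testing findings". The composite counts all-cause death as an event (protocol section IV.B, item d).

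The visible text neither says how a death is treated in the analysis of a non-fatal outcome nor names a cumulative-incidence method. SAP sections V to VII appear as bare headings and section VIII as endpoint titles, so a rule may exist there.

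**The concern.** A patient who dies cannot later have a non-fatal MI, an ACS admission leading to urgent revascularization, or a first cardiovascular test. Censoring that patient at death treats the event as still to come at the rate seen in survivors. The 1-KM curve then estimates risk in a hypothetical population in which nobody dies, and it always lies at or above the proportion of enrolled patients who actually have the event.

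The reported component and testing rates would therefore be biased in one direction, by an amount that grows with follow-up and with mortality. For testing by management strategy there is a further effect: groups with equal testing hazards but different mortality show the same 1-KM, although different shares of their patients are tested.

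**Working it through.** The documents give no event rate, mortality or sample size in the visible text, so there is no figure of the plan's own to reproduce. Every rate below is an assumption.

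**Inputs**

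- Horizon: 90 days (T = 0.25 years), 1 year and 3 years, from protocol section X.C.2.
- Three-year mortality m: assumed 1% to 5%. Patients are clinically stable, and protocol section V.D excludes "Any active, serious, life-threatening disease with a life expectancy of less than 1 year". This suggests low mortality but does not fix it.
- Three-year 1-KM value k: assumed 3% or 5% for a non-fatal component, and 20%, 30% or 50% for first test.
- Hazards constant and independent; deaths censored in the Kaplan-Meier analysis.

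**Formulas**

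- Event hazard a = -ln(1 - k)/3; death hazard d = -ln(1 - m)/3.
- 1-KM at T = 1 - exp(-aT).
- Cumulative incidence at T = a/(a + d) × [1 - exp(-(a + d)T)].

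**Worked example: k = 5%, m = 5%, T = 3.** Here a = d = 0.05129/3 = 0.01710 per year. 1-KM is 5.000%. Cumulative incidence is 0.5 × (1 - 0.95 × 0.95) = 0.5 × 0.0975 = 4.875%. The excess is 0.125 points.

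**Results at 3 years**

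| Outcome (1-KM) | Excess, m = 1% | Excess, m = 5% |
|---|---|---|
| Component 3% | 0.015 points | 0.075 points |
| Component 5% | 0.025 | 0.125 |
| First test 20% | 0.10 | 0.49 |
| First test 30% | 0.14 | 0.71 |
| First test 50% | 0.22 | 1.12 |

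In relative terms the overstatement is about half the cumulative mortality: roughly 0.5% at m = 1% and 2.3% to 2.6% at m = 5%.

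**Earlier time points, m = 5%.** At 1 year the excess is at most 0.014 points for a 5% component and 0.17 points for a 50% first-test rate (both 3-year values). At 90 days it is at most 0.001 and 0.012 points.

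**Consistency with the composite.** A component and death together cannot exceed composite MACE. With one non-fatal component plus death making up a composite C, the excess is largest when the hazard is split evenly. For C = 5%, 1-KM is 1 - √0.95 = 2.532% against a cumulative incidence of 2.500%, an excess of 0.032 points. For C = 10%, 1 - √0.90 = 5.132% against 5.000%, an excess of 0.132 points.

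**Comparison by group.** Take two groups, each with a first-test 1-KM of 50%, one with 1% mortality and one with 5%. Their cumulative incidences are 49.8% and 48.9%: a 0.9-point difference in the share tested that 1-KM does not show. At a 20% rate the difference is 0.49 - 0.10 = 0.4 points.

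**Check on the formula.** A simulation of 2,000,000 subjects with k = 2% and m = 3% gave a cumulative incidence of 1.980%, against 1.970% by formula. The difference is about one simulation standard error (0.0098 points).

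**The case against.** The strongest reply is that no error has been shown. Kaplan-Meier is named, but censoring at death is not, and the SAP sections where such a rule would normally sit are not shown. That stands. A reader might infer that the plan ignores competing risks; the documents do not support this, and the point must stay conditional.

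The second reply is that the bias is too small to matter. That largely stands too. If 1,000 to 10,000 patients are assumed, since the sample size is not visible, the 95% half-width on a 5% rate is 1.96 × √(0.05 × 0.95/n), or 1.35 to 0.43 points. This is several times the largest component excess. The 1.12-point figure needs a 50% test rate together with 5% mortality, and the 0.9-point gap also needs groups at opposite ends of the assumed mortality range. What remains is that the bias runs one way, does not shrink with sample size, and is almost free to remove.

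A reader might also infer that objectives E and G give wrong answers. They do not on this ground. Objective E concerns composite MACE, in which death is itself an event. For objective G, a log-rank or cause-specific comparison addresses whether testing hazards differ and remains valid.

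Finally, a reader might see a conflict between protocol section VII.A, which asks for observations up to withdrawal, and section VIII, which requires all MACE to be recorded, and infer that MACE is understated through informative censoring. The documents do not support this. Section VII.A does not forbid later recording, section VIII makes no exception for withdrawn subjects, and the text of section VI.G on follow-up visits is not shown. Any size would rest on invented withdrawal rates and hazard ratios.

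**Conclusion.** The point holds as a minor improvement to the estimator, and only on the condition that deaths are censored. For the two non-fatal MACE components and for first cardiovascular test, 1-KM would then overstate the share of patients with the event. The 3-year excess is about 0.02 to 0.13 points for a 5% component and 0.1 to 1.1 points for first-test rates of 20% to 50%. These figures rest on assumed constant hazards and 3-year mortality of 1% to 5%; higher mortality would raise them roughly in proportion.

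Composite MACE and all-cause death are not biased in this way. The 90-day tests of invasive procedures and revascularization are not affected, and no tested conclusion changes.

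**What to change.** In SAP section IV, add a sentence stating that non-fatal MI, unplanned ACS hospitalization leading to urgent revascularization, and first cardiovascular test will be reported as Aalen-Johansen cumulative incidence with death as the competing event. Keep Kaplan-Meier for composite MACE and all-cause death, and a log-rank or cause-specific comparison for objective G. If SAP text not shown already does this, a cross-reference from section IV is enough.

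The method is a standard software option and uses death data that the registry already collects as part of MACE. The one drawback is presentational: composite and components would use different estimators, so the tables need a note saying so.

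### SAP Secondary Endpoint 1, as titled, is not protocol secondary endpoint (a), and no visible SAP title or objective states (a), yet SAP XI declares no change from the protocol

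*Combined protocol and SAP*

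**What the plan says.** Protocol IV.B lists as secondary endpoint (a): "Rate of reclassification between Investigator management plan based on cCTA alone compared to actual clinical management within 90 days". It differs from the protocol's primary endpoint in two ways. The plan is the investigator's, not the independent committee's, and the comparator is what was actually done, not a second plan.

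SAP VIII.B.i gives Secondary Endpoint 1 this title: "proportion of coronary management plans that were changed when site reported lab FFR_{CT} coronary anatomy findings were added to the site reported lab" (the title ends by naming the cCTA results). SAP objective C, which covers plan changes, says the SAP will "report the proportion of intended strategies that were changed".

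SAP XI, the section for changes from the protocol, contains only the word None. Protocol X.E calls for an SAP that covers every primary and secondary analysis, and for any deviation to be explained in the final report. Protocol X.C.2 says that the secondary endpoints will be summarised descriptively.

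Limits of the text: SAP V to VII are bare headings, SAP VIII is a list of titles, and SAP III and X do not appear. Protocol VI.E and VI.F, on treatment recommendations and the recording of actual treatment, are named on the contents page but their text is not shown.

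**The concern.** The titles of the SAP's primary endpoint and Secondary Endpoint 1 are almost the same, with core-lab findings replaced by site-reported findings. So the SAP title keeps one of the two features that set (a) apart from the primary, the source of the assessment, and loses the other, the comparison with delivered care.

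Endpoint (a) is the protocol's only visible comparison, patient by patient, of the cCTA-alone plan with the care that followed. If the SAP list is followed as titled, the secondary results will hold a second intended-plan change rate beside the primary. A reader who relies on SAP XI could take that rate for (a), and so read a change of intention as a change of practice.

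**Working it through.** The documents state no figure for either endpoint, so there is none to reproduce. The check is a comparison of texts, followed by a bound.

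**Step 1: compare the definitions.**

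| | Protocol (a) | SAP Secondary Endpoint 1 (title) |
|---|---|---|
| Starting point | Investigator's plan on cCTA alone | Plan on site-reported cCTA findings |
| Compared with | Actual clinical management | Plan once site-reported FFRCT findings are added |
| Time window | 90 days | None stated |
| Needs an FFRCT result | No, as worded | Yes |

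The last row affects the denominator. SAP objective A will "Summarize baseline demographics and subject characteristics overall and by whether FFR_{CT} results were available", which implies that some subjects may have no result. They could count in (a) but not in Endpoint 1. The Endpoint 1 title says whose findings are used but not who makes the plan; I read it as the site's plan, by contrast with the core-lab primary endpoint.

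**Step 2: look for (a) elsewhere in the visible SAP.**

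- Objective D relates catheterization and revascularization up to 90 days to the test findings. It does not mention the cCTA-alone plan.
- "Secondary Endpoint 3: Invasive catheterization and revascularization rates 90 days post enrollment" gives rates and names no stratifier. It could be tabulated by plan, but the title does not say so.
- Objective E relates MACE to treatment plan and test findings, and objective G relates time to first test to management strategy. Neither is a plan-versus-actual change rate.
- The SAP overview aims to "describe subject outcomes, radiation exposure, and additional cardiac testing needs for subjects by whether they were planned for medication only, PCI, or CABG". It does not say whether the plan is the one before or after FFRCT, and it names no changed proportion.
- Secondary Endpoint 7 is the result of the first catheterization after baseline.

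None of these states (a).

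**Step 3: how far apart can the two quantities be?** In the same patients, with the same management categories, let A be the cCTA-only plan, B the plan after FFRCT and C the actual management within 90 days. Define:

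- c = P(A ≠ B), which is Endpoint 1
- d = P(B ≠ C), the departure of practice from the plan after FFRCT
- a = P(A ≠ C), which is protocol (a)

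A can differ from C only if A differs from B or B differs from C, so a ≤ min(1, c + d). By the same argument c ≤ a + d and d ≤ a + c, so a ≥ |c − d|. Hence |a − c| ≤ d for any number of categories.

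Both c and d are assumed here, since the documents give neither. With c = 30%:

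| Assumed d | Lower bound \|c − d\| | Upper bound c + d |
|---|---|---|
| 5% | 25% | 35% |
| 10% | 20% | 40% |
| 20% | 10% | 50% |

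To see the ends, take 100 patients with c = 30% and d = 10%. If all 10 departures are among the 30 changed plans and go back to the cCTA-only plan, then a = (30 − 10)/100 = 20%. If all 10 are among the 70 unchanged plans, then a = (30 + 10)/100 = 40%. Equality is guaranteed only when d = 0. Patients without an FFRCT result can widen the gap further.

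**The case against.** The strongest objection is that only headings can be seen. The definitions and methods that would specify (a) belong under the SAP VIII titles, and that text is not shown. Objectives E and G show that the SAP does classify follow-up by plan or strategy, so a plan-based table under Endpoint 3 is plausible. This stands. A reader might infer that the SAP has dropped (a), or has swapped one endpoint for another. The documents do not support that: they show a title that does not match and a declaration of no change, not the absence of an analysis. If unseen text under Endpoint 1 does compute (a), its title misdescribes it.

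A reader might also infer that (a) will go unreported. That is not established either, since protocol X.C.2 and X.E still require the secondary endpoints to be summarised and deviations to be explained. What remains is that an SAP recording no changes gives the final report no list of changes or reasons to draw on.

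It is tempting to widen the point: the vessel-level Secondary Endpoint 2 is not among the visible protocol items (a) to (g), and (c) and (g) are not named in any SAP title. I do not press either. The protocol text shown jumps from item (g) to V.C, so later items cannot be excluded. Protocol X.E allows for pre-specified analyses beyond the endpoint list. Parts of (g) appear in SAP Endpoints 3, 4 and 6, and (c) may be covered in text not shown.

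Finally, the bound holds for any three classifications, its ends are extremes, and its inputs are assumed. That is correct. It shows that Endpoint 1 cannot stand in for (a); it does not estimate the difference in this registry.

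**Conclusion.** The point holds in a limited form. As titled, SAP Secondary Endpoint 1 is a different quantity from protocol endpoint (a), no visible SAP title or objective states (a), and the entry in SAP XI does not fit this. The size cannot be estimated from the documents; the gap is at most d in the same patients and categories, and the percentages above are illustrations only. The endpoint is secondary and descriptive, and nothing shown makes a test, an error rate or a sample size depend on it. It should be fixed, because following the SAP as titled would report another quantity under a statement that nothing changed. Confidence is moderate, because the SAP text below the titles is not shown.

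**What to change.** 1. In SAP VIII.B, state (a) under its own title as a patient-level cross-tabulation of the investigator's cCTA-only plan against actual management within 90 days, with the changed number and percentage.
2. State the start of the window, which (a) leaves open; SAP Endpoint 3 counts from enrollment. State the denominator: all patients with a cCTA-only plan, and also the subset with FFRCT available, so that the rate can be read beside Endpoint 1.
3. If SAP text not shown already contains this table, label it as (a) and make sure that the changed proportion is reported.
4. Keep the plan-versus-plan rate as an additional endpoint.
5. Replace the entry in SAP XI with one, giving reasons, that records Endpoint 1 as added, or as replacing (a) if the sponsor does not restore (a).

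The cost is one descriptive table and a few lines of SAP wording. It depends on the eCRF holding both the cCTA-only plan and the actual treatment, which the sponsor should confirm because the text of protocol VI.F is not shown.
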